6.3.5. Handling of dropouts and missing data

a) Repositioning of visits

Not applicable.

b) Partially filled scales and missing data (other than ARSSQ and dates)

Concerning dates and ARSSQ, see §6.4.

No imputation will be done. Missing data will not be estimated and will be treated as missing data for the statistical analysis.

c) Dropouts

Patients from FAS who prematurely discontinued the study will be included in the analysis.

Except for ARSSQ and dates, no method will be applied to replace missing data.

6.4. General conventions and/or calculated variables

6.4.1. Patient reference start/end dates

For each patient, the reference dates will be the following:

- The reference start date is the date of inclusion visit.
- The reference end date is the date when patient was determined to have ended the trial.

6.4.2. Computation of a duration

The formula below will be generally used:

- Duration (in days) = Date#2 - Date#1 + 1 day

6.4.3. Missing dates of inclusion visit or end of study

Missing dates of inclusion visit and of end of study will be reviewed by the members of the Validation Committee and extrapolated using all information recorded.

AXIODIS CRO 11/47

Statistical Analysis Plan

6.4.4. Missing start/end dates of adverse events / incidents

In the following paragraphs, adverse events and incidents will be referred to as "adverse events" for ease of reading.

a) Start date

Completely missing date: it will be estimated by the reference start date.

If the day and the month are missing:

- If the year = year of reference start date, it will be estimated by the reference start date
- If the year < year of reference start date, it will be estimated by the 31st December
- If the year > year of reference start date, it will be estimated by the 1st January

If only the day is missing:

- If the month/year = month/year of reference start date, it will be estimated by the date of reference start date
- If the month/year < month/year of reference start date, it will be estimated by the last day of the month
- If the month/year > month/year of reference start date, it will be estimated by the first day of the month

If after imputation, the estimated start date is after the end date of the adverse event, it will be replaced by the end date of the adverse event.

b) End date

Note: the following rules concern events that are not "ongoing" at the end of the study.

Completely missing date: it will be estimated by the reference end date

If the day and the month are missing:

- If the year = year of reference end date, it will be estimated by the reference end date
- If the year < year of reference end date, it will be estimated by the 31st December
- If the year > year of reference end date, it will be estimated by the 1st January

If only the day is missing:

- If the month/year = month/year of reference end date, it will be estimated by the reference end date
- If the month/year < month/year of reference end date, it will be estimated by the last day of the month
- If the month/year > month/year of reference end date, it will be estimated by the first day of the month

If after imputation, the estimated end date is before the start date of the adverse event, it will be replaced by the start date of the adverse event.

AXIODIS CRO 12/47

6.4.5. Missing start/end dates of concomitant medications

Same rules as for adverse events.

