Since the computed duration in the three cases is a recovery time and not a survival time, unlike the usual case of application of Cox survival regression, the provided hazard ratios will measure the likeliness of the recovery.

Consequently, and particularly for the treatment (with Placebo as reference), a hazard ratio greater than 1 will have to be considered under a positive aspect, because it will significate that the recovery is more likely under Healsea[®] Babykids treatment than under Placebo. On the contrary, a hazard ratio lower than 1 will have to be considered under a negative aspect.

For the three durations, a forest plot of the hazard ratios and their 95% CIs from the final multivariate Cox survival regression model will be provided.

AXIODIS CRO 19/47

In addition, for the three durations, a Kaplan-Meier graph will be provided. Survival curves will be drawn by treatment group. Number of sick / symptomatic / impacted patients, number of events (recoveries) and number of censors in each arm will be displayed on the same graph, as well as the log-rank p-value.

For the same reason as above and unlike the usual case of application of Kaplan-Meier graph, if the log-rank p-value is under 5%, a survival curve for Healsea[®] Babykids group under the curve for Placebo group will have to be considered under a positive aspect, and the contrary under a negative aspect.

Patients will be analysed on the FAS.

AXIODIS CRO 20/47

Statistical Analysis Plan

10.2.3. Use and number of days of use of conventional common cold medications

A multivariate logistic regression model will be used to analyse use (yes/no) of conventional common cold medications (overall and by therapeutic class: antibiotics, antipyretics, mucolytics, decongestants, antitussives, systemic and topical corticosteroids).

BASICC

A multivariate Poisson regression model will be used to analyse the number of days of use of conventional common cold medications (overall and by therapeutic class).

The number of days of use of these medications is defined as follows:

- A day is counted when the patient used at least one of these medications this day;
- Each day is counted once, whatever the number of these medications used this day;
- The total number is the sum of all distinct days of use of these medications, from D1 to D18.

Patients will be analysed on the FAS.

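### A cold medicine that is not ongoing but has no stop date is carried to the child's end of study, which overcounts days of use (up to 15–18 days for a course started at D1)

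*SAP*

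**What the plan says.** SAP 6.4.5 covers missing medication dates in one line: "Same rules as for adverse events". The rules it borrows are in SAP 6.4.4:

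- **Scope of the end-date rules.** A note says "the following rules concern events that are not" ongoing at the end of the study.
- **Stop date wholly missing.** "Completely missing date: it will be estimated by the reference end date".
- **Only the day missing, same month.** "If the month/year = month/year of reference end date, it will be estimated by the reference end date".
- **Only the day missing, earlier month.** "If the month/year < month/year of reference end date, it will be estimated by the last day of the month".
- **Start date wholly missing.** "Completely missing date: it will be estimated by the reference start date".

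SAP 6.4.1 sets the reference start date at the inclusion visit (D1). The reference end date "is the date when patient was determined to have ended the trial", which is Visit 2 (D15–D18) for a completer.

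SAP 10.2.3 makes the number of days of use of cold medicines a secondary endpoint. It is analysed by Poisson regression, overall and by therapeutic class, over D1 to D18. Its counting rule is: "A day is counted when the patient used at least one of these medications this day". Each day counts once, however many medicines were used. SAP 6.3.5 exempts dates, along with the ARSSQ, from its general rule against replacing missing data.

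**The concern.** Setting a missing stop date as late as possible is a common cautious convention when dates serve only to classify an event. Here the length of use is itself an outcome. A medicine that is not ongoing, and so had presumably stopped before the end of the study, is given the longest course its start date allows. The error runs in one direction. Apart from the D1–D18 window, the SAP gives no cap, exclusion, sensitivity analysis or count of imputed dates by arm.

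At stake is how far the days-of-use estimates, especially in rarely used classes, reflect treatment rather than completeness of records. Better data should exist: the protocol has parents record concomitant medication in the diary daily (7.4.1) and names the diary as source document (9.1).

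**Working it through.** **Plan's own figure.** The SAP states no figure for days of use. Its only calculated figure is the primary sample size (SAP 4): 100 per arm for an effect size of 0.4 at 80% power. It reproduces: 2 × (1.960 + 0.842)² / 0.4² = 98.1, so 99 per arm; power at 100 per arm is 80.4–80.7%. I use it only for the arm size.

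**Days counted for one record.** The SAP 6.4.2 formula gives days = end day − start day + 1. With a wholly missing stop date and Visit 2 at D15–D18:

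| Start | Days counted | Excess over a true 3-day course |
|---|---|---|
| D1, or start date missing | 15–18 | 12–15 |
| D3 | 13–16 | 10–13 |
| D5 | 11–14 | 8–11 |
| D10 | 6–9 | 3–6 |

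Three things lower the excess:
- *Early withdrawal.* A child who leaves at D8 with a D1 start is counted 8 − 1 + 1 = 8 days.
- *Overlap.* Suppose one medicine was truly taken D1–D3 but has no stop date, another was taken D1–D10, and Visit 2 is at D15. The overall count becomes 15 instead of 10, an excess of 5. The class excess is still 12.
- *Known earlier month.* If only the day is missing, the stop date becomes month end, which can fall before Visit 2. As an illustration I took 89 consecutive inclusion dates from 1 March 2023, Visit 2 at D15–D18, and a true 3-day course from D1. The imputed length averages 13.3 days (range 3–18), and 61% reach 15 days or more.

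**Records split evenly between arms.** Assume 100 per arm, true means of 4.0 and 3.2 days (ratio 0.80), and an excess of 12–15 days per record:
- 5 per arm: (320 + 60)/(400 + 60) = 0.83; (320 + 75)/(400 + 75) = 0.83.
- 10 per arm: (320 + 120)/(400 + 120) = 0.85; (320 + 150)/(400 + 150) = 0.85.

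Dilution assumes equal numbers of records per arm. If they scale with true use (5 against 4), the ratio stays at (320 + 48)/(400 + 60) = 0.80, and only noise is added.

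**All records in one arm, no true difference.** With T true days per arm, k records and excess a, the unadjusted Poisson test is z = ln[(T + ka)/T] / √[1/T + 1/(T + ka)]. For a mean of 4 days (T = 400) and k = 5:
- a = 12: ratio 1.15, z = 0.140/0.0684 = 2.04, p = 0.041.
- a = 15: ratio 1.19, z = 0.172/0.0679 = 2.53, p = 0.011.

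The documents give neither the mean days of use nor the usual course length, so I varied both. Fewest records in one arm for p < 0.05 (true course 3 or 5 days from D1, Visit 2 at D15 or D18):

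| Assumed mean days per child | Records needed |
|---|---|
| 1 (for example a rarely used class) | 2–3 |
| 2 | 3–5 |
| 4 | 4–6 |
| 6 | 5–7 |

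**How likely is one-sided clustering?** If missingness is unrelated to arm, four records all fall in one arm with probability 2 × (1/2)⁴ = 12.5%, and five with 2 × (1/2)⁵ = 6.25%. Uneven but mixed splits do much less. With an assumed mean of 3 days (T = 300), a 3:1 split gives p = 0.35 (336 v 312 days) to 0.24 (345 v 315). A 4:1 split gives p = 0.16 (348 v 312) to 0.08 (360 v 315).

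**The case against.** **The link to the endpoint is not explicit.** No sentence says that dates imputed under SAP 6.4.5 generate the count in SAP 10.2.3. The latter has its own day-by-day rule. SAP 13.1 plans a listing of cold-medicine intakes separate from the general medication listing, and imputed dates are needed anyway to sort medicines into previous and concomitant. A reader might infer that the two sections contradict each other. The documents do not establish that: the first may be a general rule and the second the specific one. Feeding the count remains the natural reading, because SAP 6.3.5 exempts dates from its no-replacement rule and 10.2.3 names no other source. If the intake listing is meant to govern, the SAP should say so.

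**Such records may be few.** The investigator validates medications with the parent at Visit 2 (protocol 14.3). Monitoring checks completeness (7.5.2), and on-line checks, queries and a blind data review precede lock (9.3). This stands, and the documents give no count. A record with neither a stop date nor an ongoing flag may also be of unknown status rather than truly stopped.

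**The consequence is limited.** SAP 6.3.1 confines conclusions to the primary criterion, with secondary p-values for information only. This also stands, but the estimates are still reported and the rule still errs one way.

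**Conclusion.** The point holds with limits. Applied as written, the rule overcounts days of use for a medicine that has stopped but has no stop date, and SAP 10.2.3 does nothing to contain this beyond the D18 limit.

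Two stronger readings are tempting and not supported:
- *Every such record becomes 15–18 days.* That is a maximum. It needs a start at D1 (or a missing start date) and completion to Visit 2.
- *A handful of records will create or hide a treatment difference.* That is arithmetically possible with about 2–7 records in one arm, under assumed means of 1–6 days, true courses of 3 or 5 days and the unadjusted Poisson test. The rule is the same in both arms of a blinded trial, so the expected effect is noise and modest dilution, for example 0.80 to 0.83 with five records per arm at an assumed control mean of 4 days.

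The primary analysis is not affected. The change is worth making because it is cheap and the endpoint is named in the protocol.

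**What to change.** 1. **SAP 6.4.5:** use imputed medication dates only to classify a medicine as previous or concomitant.
2. **SAP 10.2.3:** state that days of use, overall and by class, are counted from the days recorded in the diary. When a stop date is missing, take the last diary day on which that drug was recorded.
3. **No diary day available:** keep the child in the yes/no analysis. Report days of use under two bounds: a minimum (one day, or last known use) and a maximum (the reference end date). Setting the value to missing would be worse, because it removes only users, keeps non-users at zero, and leaves the overall count undefined.
4. **Reporting:** give the number of imputed medication dates by arm.

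The cost is a short SAP amendment, one extra derivation and a small sensitivity table.

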6.4.6. Scores of ARSSQ

To compute any score of ARSSQ, if the questionnaire has been completed at a given time point except some items, these missing answers will be imputed by the last observation carried forward (LOCF).

At time points the questionnaire has not been completed at all, no imputation will be done and the score will be missing.

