7.1.3 Primary Endpoint with methods and timing for assessing recording and analysing variables

The AUC of the global score of the Acute Rhinitis Symptoms Severity Questionnaire (ARSSQ) during first 11 days of symptoms will be compared between both groups.

ARSSQ is a non-validated customized questionnaire (Appendice 1). It includes 10 items assessing symptoms, functional impairments, and global severity. Each item is scored from 0 (not present/no impact/ not sick) to 3 (severe, severe impact and very sick) for symptoms, functional impairment and global severity respectively. Parents/legal guardians will respond to questions according to the evolution of their child's symptoms. This questionnaire is based on the most common symptoms reported for children with common cold and on functional impairments easily evaluable by parents. In order to evaluate the time dependent efficacy of active/placebo, an AUC computation will be carried out.

The ARSSQ assessment will be completed in a paper diary once daily in the evening, taking into account the symptoms from the morning to the evening, within D2-D8 period. After D8, the ARSSQ will be assessed once daily until resolution of all symptoms for 2 consecutive days (question 1 of the questionnaire "not sick" ticked). At D1, the ARSSQ will be completed during the screening/inclusion visit V1. If the patient still has symptoms at V2, ("not sick" not ticked for 2 consecutive days in the previous days), the questionnaire will be also completed during the visit.

To be noticed that the duration may be censored at the end of study participation (visit V2, between day 15 and D18 after inclusion).

- 7.1.4 Secondary Endpoints with methods and timing for assessing, recording and analysing variables
- Comparison of duration of each cold symptom (questions 2 to 7 of the ARSSQ) in both groups.

For each separate symptom, the duration is defined as the number of days between Day 1 and the first day the parent/legal guardian reports the patient not having this symptom ("Not present") for 2 consecutive days.

As mentioned for primary endpoint, duration may be censored at Visit 2.

- Comparison of duration of quality-of-life impairment (questions 8 to 10 of the ARSSQ).

For each separate activity, the duration is defined as the number of days between Day 1 and the first day the parent/legal guardian reports no impact on the patient quality of life ("No impact") for 2 consecutive days.

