8.9 Management, justification, and documentation of missing data, including drop-outs

For subject who stop completing the ARSSQ before D11 (see 7.4), the Last Observation Carried Forward (LOCF) imputation will be used. Other missing data for the primary endpoint (ARSSQ) will be estimated by interpolation.

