6.4.7. AUC on global score of ARSSQ

The computation of the AUC on global score of the questionnaire will be made for patients with non-missing value at D1 and at least another non-missing time point between D2 and D11. Otherwise, the AUC will be missing.

The AUC will be computed by the trapezoidal rule from D1 to D11 (Acute Phase).

If the value at D11 is missing, then it will be estimated by the value at the last non-missing time point before D11.

AXIODIS CRO 13/47

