10. EFFICACY

10.1. Analysis of the primary efficacy criterion

The primary objective will be analysed by performing a t-test (or a Wilcoxon test if the normality assumption is not acceptable) on the means of AUC on global score of ARSSQ during the first eleven days of the study between treatment groups.

The answers of the ten items of ARSSQ are scored from 0 to 3 (0: negative answer; from 1 to 3: positive answer with an increasing severity level). See the daily report in appendix (§13.3). The global ARSSQ score at each time point is the sum of the scores to the ten items of the ARSSQ:

At each time point t: ARSSQTOT(t) =
$$\sum_{j \text{ in } \{1; ...; 10\}} ARSSQ_j(t)$$

AUC of global ARSSQ score will be computed by the method described in §6.4.7.

Patients will be analysed on the FAS and the PP Set. In each case, boxplots of the AUC on global score will be realized by treatment group. The number of available data and the p-value will be printed on the figure.

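### SAP 6.4.6 fills blank items in a completed ARSSQ by unlimited LOCF where protocol 8.9 calls for interpolation, does not declare the change, and has no rule for a blank item at D1

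*SAP*

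**What the plan says.** Protocol 8.9 has two rules for missing ARSSQ data. The first covers early stopping: "For subject who stop completing the ARSSQ before D11 (see 7.4), the Last Observation Carried Forward (LOCF) imputation will be used". The second covers everything else: "Other missing data for the primary endpoint (ARSSQ) will be estimated by interpolation".

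SAP 6.4.6 divides the problem differently. For a form filled in apart from some items, "these missing answers will be imputed by the last observation carried forward (LOCF"). It sets no limit on the number of days carried. For a form not filled in at all, "At time points the questionnaire has not been completed at all, no imputation will be done and the score will be missing".

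SAP 10.1 builds the score: "The global ARSSQ score at each time point is the sum of the scores to the ten items of the ARSSQ". SAP 6.4.7 then takes the trapezoidal AUC from D1 to D11, fills a missing D11 total with the last available total, and states that the computation "will be made for patients with non-missing value at D1 and at least another non-missing time point" in the D2 to D11 period. If this is not met, the AUC is missing.

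SAP 12 declares the replacement of the primary test and the use of question 1 in the duration rules. It does not mention item imputation.

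**The concern.** A form with a blank row is not a diary that has stopped. By the protocol's division it belongs under interpolation, yet the SAP applies LOCF and does not list this as a change. The illness is expected to resolve by itself, so item scores mostly fall. If the last tick was positive, LOCF repeats that grade on each partly completed day, even where a later answer shows that the item had come down. The repeated grade enters the ten-item sum and so the primary AUC.

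A second gap concerns D1. No earlier answer exists to carry there, and SAP 6.4.6 does not say what happens. Because the AUC requires a D1 score, one blank row at inclusion could cost a child's primary outcome. At stake are upward error in the primary variable, possible dilution of a difference, and avoidable loss of patients from the primary test.

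**Working it through.** **1. The two documents side by side**

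| Situation | Protocol 8.9 | SAP 6.4.6 and 6.4.7 |
|---|---|---|
| Questionnaire stopped before D11 | LOCF | Last total used at D11 |
| Whole day missing, later days present | Interpolation | Score stays missing; trapezoids that join the observed days amount to linear interpolation |
| Form completed, some items blank | Interpolation (other missing data) | LOCF, no limit |
| Item blank at D1 | Not addressed separately | No rule |

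The first two rows are compatible, if trapezoids join observed days (the SAP does not say so). The clear conflict is in the third row.

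**2. Scale**

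Protocol 7.1.3: "Each item is scored from 0 (not present/no impact/ not sick) to 3". Ten items give at most 30 per day. Ten one-day intervals from D1 to D11 give an AUC of at most 30 × 10 = 300. Each day from D2 to D10 has weight 1; D1 and D11 have weight 1/2.

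**3. One blank between two answers a and b**

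LOCF enters a and interpolation enters (a + b)/2, so the excess is a − (a + b)/2 = (a − b)/2.

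- For 2, blank, 0: LOCF area (2+2)/2 + (2+0)/2 = 3; interpolation (2+1)/2 + (1+0)/2 = 2; excess +1.
- Falling from mild to absent: +0.5. From severe to absent: +1.5.
- If a = b there is no excess. If Not present was already ticked, LOCF carries 0.

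**4. A longer run with a later answer**

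Item at grade s to D5, blank D6 to D10, 0 ticked at D11:

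- LOCF: 9s + s/2 = 9.5s.
- Interpolation: 4s + 6s/2 = 7s.
- Excess of LOCF over the protocol rule: 2.5s, i.e. 2.5, 5 or 7.5 points (mild, moderate, severe).
- If the symptom was in truth absent from D6, the area is 4.5s. Interpolation halves the overstatement (5s to 2.5s) but does not remove it.

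**5. A row blank to the end**

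Item at grade s to D4, blank D5 to D11:

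- LOCF gives 10s. If the symptom was absent from D5, the area is 3.5s, so the excess is 6.5s: 6.5, 13 or 19.5 points.
- This compares LOCF with an assumed truth. Interpolation has no later answer and gives no value.
- Dilution, as an illustration: a mild item last ticked at D5 on active and D7 on placebo, blank afterwards. Truth: 6.5 − 4.5 = 2.0 points apart. LOCF: 10 − 10 = 0.

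**6. A blank item at D1**

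With no value to carry, the ten-item sum is incomplete, the D1 score is naturally read as missing, and SAP 6.4.7 makes the AUC missing. The child can stay in the FAS but adds nothing to the primary test.

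The plan's sample size reproduces: n = 2(1.960 + 0.842)²/0.4² = 98.1, so 99 per arm by the normal approximation. Power at 100 per arm is 80.7% (80.4% by the noncentral t). If AUCs were lost (assumed rates):

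| AUC missing | n per arm | Power |
|---|---|---|
| 2% | 98 | 80.0% |
| 5% | 95 | 78.7% |
| 10% | 90 | 76.5% |

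If each item had an independent chance q of being blank at D1, 1 − (1 − q)^10 of children would have at least one blank: 1.0%, 4.9% and 9.6% for q = 0.1%, 0.5% and 1%. These q are assumptions.

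**The case against.** The strongest case against runs as follows.

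- **The conflict is partly interpretive.** Protocol section 8 calls itself a summary that the SAP will detail, and 8.9 does not mention items within a completed form. This stands only in part. The second rule in 8.9 covers all other missing ARSSQ data, and replacing interpolation by LOCF reverses that rule.
- **Blanks may be rare.** The form has explicit boxes for an absent symptom and for no impact, and parents are instructed at V1. One such tick makes LOCF carry 0. This stands: the frequency is unknown.
- **D1 is well protected.** The form is completed on site, congestion and one further sign must be graded for eligibility, and the eCRF has checks and queries. This stands, so D1 blanks should be rarer than diary blanks. The missing rule remains.
- **Secondary durations are largely shielded.** An imputed positive can block the zero score that ends a duration, but days from the question 1 recovery date are ignored, and SAP 6.3.1 treats secondary results as descriptive. This stands, and the point does not rest on them.

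Four stronger readings are tempting, and the documents do not support them. A reader might infer that a return to interpolation would cure trailing and D1 blanks; it cures neither. A reader might set the 13 points of step 5 beside the planned group difference; they are one child's excess against an assumed truth, and one such child in an arm of 100 moves the mean by 13/100 = 0.13 points. A reader might infer a bias in favour of one arm; the trial is double-blind, one rule serves both arms, and nothing shows a difference in blanks. A reader might take loss at D1 as a stated rule; it is an inference from the SAP's silence.

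**Conclusion.** The point holds as an undeclared departure from protocol 8.9 in the scoring of the primary endpoint. Where the last tick was positive, the item is falling and a later answer exists, LOCF overstates the AUC relative to the protocol rule. The excess is 1 point for a single blank between 2 and 0, and 2.5 to 7.5 points for the five-day run in step 4, on a scale of 300. The expected effect is upward error in both arms and possibly some attenuation. Its total size cannot be given, because it depends on how often rows are left blank.

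The D1 gap is a separate omission. The conclusion that the AUC would be missing rests on the natural reading of SAP 6.4.6 with 6.4.7. The sample size statement itself is correct, and any loss of power depends on the assumed rates above. The point deserves correction because the repair is nearly free; it gives no ground to call the primary comparison invalid.

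**What to change.** 1. In SAP 6.4.6, impute a blank item by linear interpolation between that child's nearest earlier and later answers to the same item, in line with protocol 8.9. Keep LOCF only where no later answer exists.
2. State a rule for an item blank at D1, so that one blank row does not by itself make the AUC missing.
3. List in SAP 12 any departure from protocol 8.9 that remains.
4. Report the number of blank items by arm, and add a sensitivity analysis for trailing and D1 blanks, for example with trailing blanks scored 0.

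The cost is some SAP wording and a little more programming. No new data are needed.
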